These applications were developed by RAND specifically for this project, and are standalone counter applications that observers will use to record park utilization. There are two park counters, one records gender, age, and activity level, and one records gender by race/ethnicity. See Appendix A for a screenshot and further description of each counter.

Equipment Management and Distribution

The RAND supplied field laptop (Dell E6410), iPads not in use, and park folders will be stored at AltaMed. Promotoras are to charge their own iPad overnight after conducting park observations, or drop off at AltaMed for charging if they are not scheduled to work in parks.

DATA COLLECTION

The two primary pieces of data collection are park observations and interviews. Observations are conducted according to SOPARC protocols, on three weekdays and three weekend days spread over

five to six months. Observations occur three times per day at 3-hour intervals (e.g., 12pm, 3pm, 6pm). A team of two *promotoras* is assigned to collect data at a park, though at the beginning of the data collection phase two teams of two were assigned for reliability assessment purposes.

Prior to beginning data collection project managers will visit each park and create a target area map (see appendix B for a park mapping guide). On the first day of data collection a project manager meets the team at the park to review the park map and deliver any needed equipment and/or materials. On subsequent data collection days a project manager will meet the team if they have not observed at that park previously, otherwise the team will proceed according to the schedule and data collection protocols.

There are two primary types of interviews; targeted park user interviews (people in the park) and randomly selected residents (people living within one mile of the park). If *promotoras* are unable to contact residents at home for accessibility, safety, or other reasons, station interviews will be conducted. Station interviews are administered to a convenience sample of individuals who are recruited at high pedestrian spots (e.g., transit stations, storefronts, etc.) in neighborhoods within one mile of the park. The same instrument is used for the three types of interviews (see appendices C and D for English and Spanish versions). Data collectors will record an observed body type for each respondent using an image of body type categories (see appendix E).

Participant Recruitment and Protection

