In order to obtain random samples, park user and household interview respondents are recruited according to established protocols. Park users are recruited according to set quotas aimed at gaining participants equally distributed by gender, activity level, and age. Household respondents are recruited using a random selection of residential addresses. Recruitment protocols for both interview types can be found in appendices F and G.

Data collectors will obtain oral consent (appendix H) prior to administering the interview, and provide a small incentive upon completion. They also will have available a project summary sheet (in English and Spanish) that lists the project managers contact information if respondents request additional information (appendix I). If a respondent appears in need of immediate mental health services, data collectors will provide contact information for appropriate emergency services (appendix J) and inform park staff.

Park Use Counters

The 12-button age/activity counter app is designed to capture the number of park users by physical activity level and age group, i.e., observers will record physical activity and age group simultaneously for each individual park user within a defined target area. The app is for counting purposes only and the data must be entered into a separate Pendragon form described below.

The counter consists of 12 buttons arranged in four columns (age group) and three rows (activity level). Buttons are color coded by age group.

[figure not shown]
On the bottom of the app screen are summary and other functions including:

1. Observation Count: Returns a summary of the current counts.
2. Reset Counters: Returns all fields to a 0 value.
3. Edit Previous Record: Allows the observer to edit the immediately preceding entry.

[figure not shown]
Installation on an iPad

These instructions are for an iPad running iOS 7, and may be different for other devices or operating system. Safari was used to load the counters and the bookmarking and icon creation process described here may vary in other browsers.

1. Connect the device to a wireless network.
2. Open Safari on the device and navigate to <http://mmicdata.rand.org/parkcounter>.
3. Tap the 'Age/Activity' tab.

4. After arriving to the counter screen, tap the save icon on the toolbar, and choose “Add to Home Screen.” This will install the icon on the home screen.

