Appendix C: Park user and household survey (English)

Revised 6/11/13

NEIGHBORHOOD PARKS

Interviewer: _____ Date: _____ Time: _____ AM / PM (Circle one)

Participant type: Park user ¼ mile resident ½ mile resident 1 mile resident
 Station ¼ mile Station ½ mile Station 1 mile

Gender: Male Female Age: _____ Activity level: Sedentary Active

INTERVIEWER TO READ STATEMENT: This survey is mainly about _____ [park name]. Please think about this park when you answer the questions.

1. How many children under the age of 18 do you have?

_____ (insert number)

2. How do you describe yourself in terms of race or ethnicity? (Check one)

- Latino Asian / Pacific Islander
- White American Indian / Alaska Native
- Black Other _____

3. How often do you come to this park? (Check one)

- Daily
- A few times a week
- Once per week
- A couple times per month
- Monthly
- A few times a year
- This is the first time
- Never [skip to #10]

4. How many times did you visit this park within the past SEVEN days?

_____ (insert number)

- Don't know

5. On a typical day when you go to the park, how long do you stay there?

(Check one)

- 0-30 minutes 2 – 3 hours
- 31-60 minutes > 3 hours
- > 1 hour, but < 2 hours

6. When was the first time you came to this park?

(Check one)

- Today
- This month
- In the past 6 months
- Between 6 - 11 months ago
- Between 1 - 2 years ago
- More than 2 years ago

7. How do you usually get to the park?

(Check one)

- Walk
- Bike
- Car
- Bus or other public transportation
- Other _____

8. What do you usually do while at this park?

(Check all that apply)

- Aerobics Meet friends
- Baseball/softball Playground
- Basketball (indoors) Sitting in park
- Basketball (outdoors) Skating
- Celebrations or picnics Soccer
- Classes Swimming
- Frisbee Tennis
- Gymnasium activity Volleyball
- Gymnastics equipment Walking
- Handball Walking with dog
- Other _____

9. When you are at this park, do you run into people you know? (Check one)

- Yes, often Rarely
- Yes, sometimes No, not at all

10. If you do not visit this park, why not?
(Only ask this question if the respondent answered "Never" to question 3)

11. How would you grade the park staff with respect to their helpfulness, friendliness, and professionalism?
(Check one)

A D
 B F
 C Don't know the staff

12. In general, how safe do you feel the park is?
(Check one)

Very safe
 Safe
 Not very safe
 Not safe at all

13. Where do you usually exercise? *(Check one)*

I don't usually exercise
 Park
 Home

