| Adult sport league |  Yes |  No |
| Dance classes |  Yes |  No |
| Fitness / aerobics class |  Yes |  No |
| Organized walks / hikes |  Yes |  No |
| Park events (e.g., fair) |  Yes |  No |
|  Other _____ | | |

23. What is the nearest intersection to your home?

(INTERVIEWER NOTE: Please indicate complete street name (i.e., 49th Place or 49th Street). Also verify that these streets intersect!)

Major Street _____

Cross Street _____

24. Using the map provided, indicate in which buffer the respondent's home is located.

- 0 - ¼ mile ½ - 1 mile
 ¼ - ½ mile 1+ miles

25. How long have you lived at your current address? (Check one)

- Less than 1 year
 1 - 2 years
 > 2 years, but < 5 years
 Between 5 - 9 years
 10 years or more

INTERVIEWER TO READ: Because we know that park use can be affected by whether you work, your health, and your exercise habits, we have a few questions about those. Please remember that your answers are anonymous.

26. Are you currently: (Check all that apply)

- Working full-time
 Working part-time
 Self-employed
 Unemployed, looking for work
 Retired
 Disabled
 A student (full or part time)
 A stay-at-home parent
 Other _____

27. What is your highest level of education completed?

(NOTE: If respondent attended school outside of the U.S. indicate the closest equivalent) (Check one)

- 6th grade or less
 7th-11th grade
 High school graduate or GED
 Some college (but no degree)
 Associate's degree (AA)
 Bachelor's degree (BA, BS)
 Some graduate school or graduate degree

28. How many times per week do you engage in physical activities such as walking, cycling or any activity that causes increased breathing or heart rate, leg fatigue, or causes you to perspire?

- 0 [skip to 30] 5
 1 6
 2 7 or more
 3 Don't know
 4

29. What is the usual length of these physical activities? (Check one)

- Less than 5 minutes
 > 5, but < 15 minutes
 15-30 minutes
 > 30, but < 45 minutes
 More than 45 minutes

30. Do you engage in physical activities as part of your work on a regular basis? (Check one)

- Yes No

31. How much time outside of work do you spend watching television, DVDs or videos, playing video games, or using a computer on an average day? (Check one)

- 0 - 60 minutes

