Appendix G: Household interview recruitment guide

Household Sample

Interviewers will survey residents living at designated addresses within one quarter (1/4 mile), one half (1/2 mile), and one (1 mile), of the park. RAND will identify residential addresses within each of these three different distance areas and provide them to Interviewers by the first day of each park observation. The goal is to interview members of 10 households in each stratum, or complete 30 interviews.

The Interviewer (you) will need to determine if those addresses are appropriate for including in the study. In some cases, multiple residences may be associated with a single address (e.g. apartment buildings) or the address may not be valid (e.g., commercial buildings, vacant lots, condemned home). You must follow the established protocols to ensure that the interviewing methods meet scientific research criteria.

Selecting Apartments

When the provided address is to an apartment building, individual units are determined as follows:

1. The **1st time** you encounter this scenario, take the stairs to the **second floor** of the building. Approach the **first apartment to the right**. This protocol should be followed for all oddly numbered subsequent occurrences (3rd time, 5th time, 7th time, etc.). [If the apartment building is a single story, follow the directions in #2.]
 - a. On the Household Interview Log, enter the apartment number next to the printed address AND note that the apartment is on the second floor.
2. The **2nd time** you encounter this scenario, select the **first apartment to the right** on the **first floor** of the building. This protocol should be followed for all evenly numbered subsequent occurrences (2nd time, 4th time, 6th time, etc.).
 - a. On the Household Interview Log, enter apartment number next to the printed address AND note that the apartment is on the first floor.

Selecting Freestanding Units

When there is more than one freestanding unit at the provided address, determine which unit to approach as follows:

1. The **1st time** you encounter this scenario, select the **first unit** you approach when walking onto the property. This protocol should be followed for all oddly numbered subsequent occurrences (3rd time, 5th time, 7th time, etc.).
 - a. On the Household Interview Log, enter the unit number (e.g., Unit A or front house) next to the printed address.

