Appendix L: Data Log

Two data logs will be used in each park (or four during reliability data collection periods). The first page (Parks Data Log) summarizes data collection to date, while the second (Park User Interview Log) and subsequent pages are used to record daily park user interviews.

PARKS DATA LOG
 ____ of ____

Park: _____

Name	Date & Day of week	Park interviews		Household interviews		Station interviews	
		iPad	Paper	iPad	Paper	iPad	Paper
Sub-total							
TOTALS							

Park User Interview Log

Park name: _____

Date: _____

Promotora name: _____

#	Target Area	Gender M = Male F = Female	Race/Ethnicity L = Latino B = Black W = White O = Other	Age Group Ad = Adult Sr = Senior	Activity Level S = Sedentary A = Active	Outcome I = iPad P = Paper R = Refuse	Comments
1		M F	L B W O	Ad Sr	S A	I P R	
2		M F	L B W O	Ad Sr	S A	I P R	
3		M F	L B W O	Ad Sr	S A	I P R	
4		M F	L B W O	Ad Sr	S A	I P R	
5		M F	L B W O	Ad Sr	S A	I P R	
6		M F	L B W O	Ad Sr	S A	I P R	
7		M F	L B W O	Ad Sr	S A	I P R	
8		M F	L B W O	Ad Sr	S A	I P R	
9		M F	L B W O	Ad Sr	S A	I P R	
10		M F	L B W O	Ad Sr	S A	I P R	
11		M F	L B W O	Ad Sr	S A	I P R	
12		M F	L B W O	Ad Sr	S A	I P R	
13		M F	L B W O	Ad Sr	S A	I P R	
14		M F	L B W O	Ad Sr	S A	I P R	
15		M F	L B W O	Ad Sr	S A	I P R	

At the end of the day, record the number of park user interviews completed in each category. Add the sub-total from the preceding day to your daily total, and enter the sum in the appropriate sub-total box.

[figure not shown]
	Female		Male	
	Sedentary	Active	Sedentary	Active
Daily total				
Sub-total				

Note that this page is to be duplicated for each day of data collection (i.e., each data collector should complete one of these pages for each day of data collection in every park. A single packet can be made with one Parks Data Log followed by six park user interview logs (possibly more for makeup days).

[figure not shown]

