We used negative binomial distributions in the DID models due to the sizable heteroscedasticity in park use outcomes (Cohen et al., 2012). Effects of the intervention were presented in the scale of multiplicative scale (i.e., % changes) in these models. We also examined the outcomes by two age groups (youths versus adults). In analyzing survey outcomes, we controlled for respondent-level covariates to reduce estimation biases because randomization was not at the individual level, including gender, age, education level, obesity status, address buffer (<.25 mile, .25 to .5 miles, and .5 miles to 1 mile to park), self-rated health, perception of park safety, primary language, and having children under 18 years old. All statistical models were fitted in SAS 9.4. We also conducted sensitivity analyses using robust standard errors for park clustering effects and alternative scale for transformed mean outcomes (log or logit) wherever appropriate. The main findings were not sensitive to alternative model specifications.

Statistical power: This study was powered to detect a small to medium standard effect size under the regular setting of two-sided p -value <0.05 and power >0.80 . With 12 parks in each study arm and the extensive repeated measurements in each park (18 hourly observation per wave for two waves), we can detect a difference of 0.34 times standard deviation (SD) between any two arms when the intra-class correlation is no greater than 0.10. Based on historic data from previous studies (average park use 55 persons/hour, $SD=35$, approximately)(Cohen et al., 2013) meant that we could detect an additional 11.9 persons/hour. Because most survey outcomes were categorical, we used a two-sample z -test for calculating the detectable effect size for survey analysis. With 20 surveys in each wave and in each park's neighborhood, we could detect a difference of 15 percentage points for a binary outcome with a baseline prevalence between 20% and 80%. The detectable effect size is even smaller if the baseline prevalence rate is very high or very low (e.g. $<20\%$, or $>80\%$).

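### The survey models neither adjust for interview type nor test sensitivity to it, although convenience station interviews can replace random-address household interviews

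*Protocol*

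**What the plan says.** **Household sample.** The protocol (Participant Recruitment and Protection) says: "Household respondents are recruited using a random selection of residential addresses". Appendix G sets the target per park over three distance bands: "The goal is to interview members of 10 households in each stratum, or complete 30 interviews".

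**Fallback.** The Data Collection section says that where field staff are "unable to contact residents at home for accessibility, safety, or other reasons, station interviews will be conducted". It then describes the method: "Station interviews are administered to a convenience sample of individuals who are recruited at high pedestrian spots". The recruitment spots lie within one mile of the park. Appendices F and G give selection rules for park users and households. Neither gives rules for station interviews, and no limit on their number is stated.

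**Recording.** The participant-type line of the survey form (Appendix C) lists resident categories and, separately, "Station ¼ mile Station ½ mile Station 1 mile". The data log (Appendix L) also counts station interviews in their own columns.

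**Analysis.** The SAP models the effect as a wave-by-arm interaction, with park random effects. For survey outcomes it states: "we controlled for respondent-level covariates to reduce estimation biases because randomization was not at the individual level". The covariates it then names are gender, age, education, obesity status, distance band (three levels, ending at one mile), self-rated health, perceived park safety, language and having children under 18. Interview type is not among them. The sensitivity analyses cover robust standard errors and alternative outcome scales only.

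**The concern.** People stopped on foot at transit stops or storefronts may differ from people found at random addresses in how often they visit the park, what programmes they know of and how much they exercise. Appendix K says the data carry no personal identifiers, so respondents cannot be linked across waves and each wave is a fresh cross-section. The survey contrast therefore relies on the mix of respondents not shifting differently by arm. The SAP accepts this principle when it adjusts for respondent characteristics, yet the one variable that describes how the respondent was sampled is left out.

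What is at stake is the survey evidence, including Aim 2 on perceived safety. Energy expenditure and the count of park users come from direct observation and do not depend on who was interviewed.

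**Working it through.** **1. When bias arises.** Let H be the mean outcome for household respondents, s the station share, and g the station-minus-household gap, taken as constant. The mean in arm a at wave w is H(a,w) + s(a,w) × g. Taking differences between waves and then between arms A and B gives

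bias = g × [(sA2 − sA1) − (sB2 − sB1)].

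Three hypothetical cases with g = 10 points:

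| Arm A share | Arm B share | Bias |
|---|---|---|
| 40% → 40% | 10% → 10% | 10 × (0 − 0) = 0 |
| 10% → 30% | 10% → 30% | 10 × (0.2 − 0.2) = 0 |
| 10% → 30% | 10% → 10% | 10 × (0.2 − 0) = 2 points |

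A difference in level between arms does no harm if it is stable, and a common drift does no harm. Only a differential change matters. On a log or logit scale the cancellation is approximate.

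**2. The SAP's own yardstick.** The Statistical power paragraph gives 15 points for a binary survey outcome, with 12 parks per arm and 20 surveys per park per wave. That is 12 × 20 = 240 per arm per wave. At 50% prevalence, two-sided 0.05 and power 0.80, the simple two-sample formula gives (1.96 + 0.84) × √(2 × 0.25/240) = 12.8 points without clustering. An assumed intra-class correlation of 0.02 (not stated for surveys) gives a design effect of 1 + 19 × 0.02 = 1.38, and 12.8 × √1.38 = 15.0. So 15 points is a reasonable reference.

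**3. Illustrative size.** Neither g nor the station share is in the documents. With assumed values:

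| Gap | Differential change 10% | 20% | 40% |
|---|---|---|---|
| 5 points | 0.5 | 1 | 2 |
| 10 points | 1 | 2 | 4 |
| 20 points | 2 | 4 | 8 |

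**4. What that does to a test.** A 15-point detectable difference implies a standard error of about 15/2.80 = 5.4 points. The chance of a false positive is P(|Z + bias/SE| > 1.96):

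- 0.5 points: shift 0.09 SE, 5.1%, negligible
- 4 points: shift 0.75 SE, about 12%
- 8 points: shift 1.49 SE, about 32%

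The 15-point figure compares two proportions. A four-cell difference-in-differences at 50% prevalence has a standard error of at least √(4 × 0.25/240) = 6.5 points if observations are independent, which would make these inflations smaller.

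**5. Is anything in the plan a substitute?** Distance band, age, education and language may absorb part of g. A park random intercept removes stable differences between parks, not a change in sampling method within a park. Robust standard errors change the variance, not the estimate.

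**The case against.** The strongest reply is that no mechanism makes the change differ by arm. Parks were randomised, and exercise classes or a loyalty scheme have no obvious bearing on whether someone can be interviewed at home. A differential change would then be chance imbalance across 12 parks per arm, which park-clustered standard errors would partly reflect. Appendix G also limits the need for the fallback through four contact attempts and rules for replacement addresses. This stands, and it is why no bias is asserted. It does not remove the case for adjustment: a chance imbalance still moves the estimate obtained, and the plan does not report the shares that would show whether it occurred. The SAP's covariate list opens with a word that could mean it is not exhaustive, but interview type appears nowhere else in the SAP.

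Three stronger readings are tempting and are not supported.

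- **That the switch is driven by the safety outcome.** Safety is one trigger of several, and the list ends with other reasons. In Appendix G the concern is the interviewer's own safety at an address. That may go with neighbourhood crime, but it is not the perceived park safety that the survey measures.
- **That people living more than a mile away are in the resident models.** Survey item 24 does have a category beyond one mile, but the same form serves park users, who may live anywhere. The protocol defines residents as living within a mile, and a three-level distance band fits a dataset from which others were already removed. What is missing is a written exclusion rule.
- **That station interviews are known to be in the models.** The SAP speaks of resident respondents and does not say which interview types this covers. The protocol makes station interviews the stand-in for home interviews, so inclusion is the natural reading, but it is not stated.

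**Conclusion.** The point holds as a gap in the survey analysis: a recorded change of sampling method is neither adjusted for nor tested. Bias is possible only if the station share changes differently by arm and station and household respondents differ after adjustment for the named covariates. The size is unknown. The range of 0.5 to 8 points rests wholly on assumed gaps of 5 to 20 points and assumed differential changes of 10% to 40%. Its upper end needs both extremes together, and every value is below the 15-point detectable difference. Only survey outcomes are concerned. The observed energy expenditure and user counts are untouched.

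**What to change.** - Add interview type (household or station) as a covariate in the survey models.
- State which interview types form the survey analysis set, and report the station share by arm and wave.
- Repeat the survey analyses on household interviews only, as a sensitivity analysis.
- State that respondents living beyond one mile are excluded from the resident analysis, in line with the three-level distance band.

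The SAP is written in the past tense, so this means clarification and re-running models on variables that the form already has. The cost is one more parameter. The household-only analysis loses respondents from less accessible areas and so shifts the population it describes, which is why it should stay a sensitivity analysis and not replace the main one.
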